8.1.2. Procedures for AE Reporting by the Investigator

AEs will be monitored throughout the study and will be recorded on the eCRF with the date and time of onset, date and time of resolution, severity, seriousness, causality (relationship to use of IP), treatment required, and the outcome.

To elicit AEs, simple questions with minimal suggestions or implications should be used as the initial questions at all evaluation points during the trial. For example:

- How have you felt since your last assessment?
- Have you had any health problems since your last assessment?

The severity of each AE should be categorized as mild, moderate, or severe.

The causality of use of IP in relation to the AE will be assessed by the Principal Investigator after careful medical consideration and categorized as unrelated, unlikely, possible, probable, or definite.

If an AE occurs, the Investigator will institute support and/or treat as deemed appropriate.

If a non-SAE is unresolved at the time of the last day of the study, an effort will be made to follow up until the AE is resolved or stabilized, the subject is lost to follow-up, or there is some other resolution of the event. The Investigator should make every attempt to follow SAEs to resolution.

8.1.3. Serious Adverse Event Reporting by the Investigator

Serious Adverse Event Reporting

It is the responsibility of the Investigators or their designees to report any event of this nature to the Sponsor or a designee within 24 hours of the event being brought to the Investigators' or their staffs' attention. It is also the responsibility of the Investigator to report all SAEs reported at their site to their Institutional Review Board (IRB), as required. The Investigator should make every attempt to follow all SAEs to resolution.

The following information should be provided when an SAE is reported to the Sponsor or designee:

1. Protocol Number
2. Site Number
3. Subject Number
4. Subject Demographic information, including:
 - Date of Birth

- Sex
- Race

5. IP start date
6. Date of last dose of IP
7. Date investigational product reinitiated (if investigational product interrupted)
8. SAE information, including:
 - SAE term (diagnosis only; if known or serious signs/symptoms)
 - Description of SAE/narrative
 - Date/time of onset
 - Severity
 - Outcome
 - Date/time of resolution or death (if duration < 24 hours)
 - Relationship to IP
 - Action taken with IP
9. Criteria for classifying the event as serious, including whether the SAE:
 - Resulted in death.
 - Was life-threatening
 - Required inpatient hospitalization
 - Prolonged inpatient hospitalization
 - Resulted in a persistent or significant incapacity or substantial disruption of the ability to conduct normal life functions.
 - Was a congenital anomaly/birth defect
 - Important medical events that may not result in death, were not life-threatening, or did not require hospitalization may be considered serious when, based upon appropriate medical judgment, they may jeopardize the subject or subject may require medical or surgical intervention to prevent one of the outcomes listed in this definition. Examples of such medical events include allergic bronchospasm requiring intensive treatment in an emergency room or at home, blood dyscrasias or convulsions that do not result in inpatient hospitalization, or the development of drug dependency or drug abuse.
10. Concomitant medications

11. Relevant history
12. Possible causes of SAE other than IP
13. Copy of AE page from the eCRF

NOTE: If a SAE occurs in any study involving VVN001 or Vehicle that is unexpected and is determined to be definitely related, probably related or possibly related to IP, all sites will be notified by the Sponsor and each site should report it to its IRB.

9. STATISTICS

9.1. STATISTICAL METHODS

9.1.1. Analysis Populations

The following analysis populations will be considered:

Full Analysis Set (FAS) – The FAS includes all randomized subjects. The efficacy analysis will be performed on the FAS. Subjects in the FAS will be analyzed as randomized.

Per Protocol Set (PPS) – The PPS includes subjects in the FAS who do not have significant protocol deviations and who complete the study. Protocol deviations will be assessed prior to database lock and unmasking. The PPS will be analyzed using observed data only for efficacy variables. Subjects in the PPS will be analyzed as treated.

Safety Set (SAF) – The SAF includes all randomized subjects who have received at least one dose of the IP. The SAF will be analyzed for all safety assessments. Subjects in the SAF will be analyzed as treated.

The statistical analysis of safety data will be performed for the SAF. The analysis of baseline and efficacy data will be performed for the FAS. Sensitivity analyses may be performed on the PPS.

9.1.2. Subject Disposition, Demographic and Background Characteristics

Subject disposition, demographic characteristics, and background variables will be summarized by treatment group.

9.1.3. Analysis of Efficacy effects

To assess whether VVN001 is more effective than Vehicle, exploratory efficacy will be performed. The unit of analysis for ophthalmic efficacy measures depends on the measure itself. Some endpoints will be analyzed per subject whereas others will be analyzed per eye (study eye and non-study eye, where study eye is defined in Section 4.4).

The following parameters will be assessed per eye (study eye and non-study eye):

- Total and Individual CFS score
- Tear production (Schirmer test without anesthesia, mm/5 min)

The following parameters will be assessed per subject (one score for both eyes):

- VAS for Eye Discomfort
- VAS for Eye Dryness
- SANDE

All efficacy parameters will be analyzed as continuous data. Analysis will be performed at each timepoint using summary statistics as well as a longitudinal model as appropriate.

Analyses of all efficacy endpoints will be done using the FAS. Analyses on the study eye will be repeated for all non-study eye as supportive analyses. Analyses may also be repeated on the PP set.

The primary analysis will utilize a repeated measures mixed model where the dependent variable is the change from baseline score, treatment group is a fixed effect, baseline score is a covariate, and visit is a repeated measure on subject. The repeated measures mixed model is utilized to account for the effect of missing data under the assumption that the data are missing at random. Least squares means will be used to test each concentration of VVN001 to vehicle. Sensitivity analyses for the primary endpoint will be performed using last observation carried forward (LOCF) as well as observed data only.

In order to minimize the impact of multiplicity, the following hierarchical tests will be conducted:

- 1) Primary (iCFS on Day 84, study eye) high concentration vs. vehicle
- 2) Primary (iCFS on Day 84, study eye) low concentration vs. vehicle
- 3) Key secondary (Eye Dryness VAS on Day 84) high concentration vs. vehicle
- 4) Key secondary (Eye Dryness VAS on Day 84) low concentration vs. vehicle

The comparisons will be conducted at the 5% significance level. Each comparison will be made in order until $P > 0.05$. If $P \leq 0.05$, the comparison is statistically significant and testing is continued.

The planned analyses for all outcomes will be described in detail in the SAP, which will be finalized and submitted prior to database lock.

9.1.4. Analysis of Safety

Analysis of safety data will be presented for all subjects in the Safety Population. AEs will be coded using Medical Dictionary for Regulatory Activities (MedDRA, most current version) and categorized by system organ class using preferred terms. AEs will be tabulated by treatment group with respect to their Severity and relationship to the IP. Ophthalmoscopy findings will be summarized descriptively. IOP measurements, BCVA, dilated ophthalmoscopy, external eye exam and slit-lamp biomicroscopy will be summarized as safety outcomes.

The primary safety analysis will summarize ocular and non-ocular treatment-emergent adverse events (TEAEs) using discrete summaries at the subject level by system organ class and preferred term for each treatment group. A TEAE will be defined as occurring after the first dose of IP. Serious adverse events (SAEs) and treatment-related ocular and non-ocular TEAEs will be summarized similarly. Ocular and non-ocular TEAEs will also be summarized by severity and relatedness.

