4.7.2. Dosage and Administration

VVN001 will be administered as a topical ophthalmic solution. Subjects will be randomized to receive one of the following three treatment groups:

- Group A: 1% VVN001 Ophthalmic Solution BID
- Group B: 5% VVN001 Ophthalmic Solution BID
- Group C: Vehicle BID

Justification for Dose

The concentrations of VVN001 Ophthalmic solution and dosing schedule were chosen based on non-clinical pharmacokinetic (PK) and toxicology studies and data reflecting relative safety multiples. For details on the pharmacokinetic and toxicology studies and the respective safety multiples, see the Investigator's Brochure.

IP Dispensation Instructions

At Visit 1, eligible subjects will receive one kit of Single-Masked Vehicle Run-In.

At Visit 2, randomized subjects will be assigned to an IP Kit which contains 4 weekly cartons of Double-Masked IP (VVN001, 1%, VVN001, 5% or Vehicle). The kit will contain a sufficient supply of IP for approximately 28 days of dosing. Subjects will return the used IP at Visit 4 and will receive a second supply of IP which will be sufficient for another approximate 28 days of dosing. The subject will again return the used IP at Visit 5 at which time they will receive the last kit of IP which will contain a sufficient supply for dosing through the remaining duration of the study.

Timing of Self-Administration

IP (VVN001, 1%, VVN001, 5% or Vehicle) will be administered to the ocular surface twice daily as a single drop in each eye administered morning and evening. The subject should be instructed to ensure they instill at least one drop in each eye per each administration.

The first dose of Single-Masked Vehicle and the first dose of Double-Masked IP (VVN001, 1%, VVN001 5% or Vehicle) will be self-administered by the subject under supervision of the site staff. This will be considered the morning dose for that day.

Following Visit 1, the subjects will self-administer the second dose of Single-Masked IP in the evening and will be instructed to self-administer one drop into each eye bilaterally BID for approximately 14 days. Following Visit 2 the subjects will be instructed to self-administer the second

dose of Double-Masked IP in the evening and will be instructed to self-administer IP BID instilled into each eye bilaterally for approximately 84 days.

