4.8. PREPARATION/STORAGE AND ACCOUNTABILITY

4.8.1. Product Appearance/Packaging and Labeling

VVN001 Ophthalmic solution is a sterile solution for topical application to the eye at either 1% or 5%. Placebo for VVN001 ophthalmic solution is a matching sterile vehicle solution.

Single-Masked and Double-Masked IP is contained in 3 mL single-use droppers. Subjects will be instructed to instill one drop in each eye and then place the used dropper back into the kit. All investigational products kits are labeled with the following information:

- Product name, Batch number, Protocol number, Kit number, Storage instructions, Sponsor city and state, manufacturing date • “New Drug - Limited by Federal (United States) Law to investigational Use”

Each Single-Masked Kit will contain two weekly cartons with 16 single-use droppers packaged in a weekly use kit (carton box with dividers) by VivaVision, or designee.

Each randomized, Double-Masked monthly IP kit contains four weekly cartons with 16 single-use droppers packaged in a weekly use kit (carton box with dividers).

Each site will be provided with emergency back-up kits of Double-Masked IP in case of contamination or other loss. The investigational sites will be directed to assign specific emergency kits to individual subjects using the Interactive Web Response System (IWRS).

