6. STUDY PROCEDURES

6.1. VISIT DESCRIPTIONS

6.1.1. Visit 1 (Screening): Day minus 14 (± 2 days) prior to Visit 2

The following will be performed/assessed in the order suggested below and all ocular assessments will be conducted in both eyes (as applicable):

- Explain the purpose and conduct of the study to the subject, answer the subject's questions, and obtain written informed consent.
- Obtain information including demographics, concomitant medications, ocular and systemic medical and medication history and surgical history.*
- Assess for prior AT use.
- Evaluate eligibility
- A Screening Identification (ID) should be assigned to the Subject once any Visit 1 procedures (other than Informed Consent Form (ICF)) are performed.
- Subject-rated symptom assessments (in this order):
 - Individual eye dryness and discomfort symptom assessment via VAS
 - SANDE
- Urine Pregnancy Test (UPT) for all eligible women of childbearing potential.*
- Safety Lab Draw (Hematology, Serum Chemistry, Serology and Urinalysis).*
- BCVA
- Slit-lamp biomicroscopy and external eye exam
 - Includes evaluation of conjunctival hyperemia
- CFS (Wait 15 minutes prior to performing Schirmer test)
- Unanesthetized Schirmer test
- IOP
- Dilated Ophthalmoscopy
- Determine if the subject is eligible to continue in the study. Do not continue screening any subject who does not meet eligibility requirements. Any subject who does not meet eligibility requirements will be designated as a Screen Failure.
- If the subject is qualified, a kit containing a two-week supply of Single-Masked Run-In will be provided.
- Subject will self-administer first dose of Single-Masked IP observed by trained study staff.
- Administer the Drop Comfort Tolerability Assessment at 1-minute and 5-minutes post dose.

- Dispense daily dosing diary.
- Instruct the subject to discontinue using all prohibited medications for the remainder of the study and schedule to return to the clinic for Visit 2 in two weeks.

*May be performed at any time during the visit in order to facilitate subject and site schedules.

6.1.2. Visit 2 (Randomization): Day 1

Visit 2 will occur 14 (± 2 days) after Visit 1 (Screening). The following will be performed/assessed in both eyes (as applicable):

- Evaluate continued eligibility
- Subject-rated symptom assessments (in this order):
 - Individual eye dryness and eye discomfort symptom assessment via VAS
 - SANDE
- Use of any concomitant medications since the last visit

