- Occurrence of any AEs since the last visit *
- BCVA
- Slit-lamp biomicroscopy and external eye exam
 - Includes evaluation of conjunctival hyperemia
- CFS
- Wait 15-20 minutes after CFS before proceeding
- Unanesthetized Schirmer test
- IOP
- Collect used Run-In, Daily Dosing Diary and check compliance
- Determine if subject is eligible for randomization

For eligible subjects, the following is the process regarding administration of Double-Masked IP whereby the trained site staff will conduct the following procedures:

- Enter subject information into IWRS to determine randomization code and Kit Number.
- Subject will self-administer first dose of Double-Masked IP observed by trained study staff.
- Administer the Drop Comfort/Tolerability Assessment at 1-minute and 5-minutes post dose.

- Assess for occurrence of any IP related AEs
- Dispense 4 weeks supply of double masked IP and Daily Dosing Diary
- Collect used Single-Masked IP kit
- Schedule the subject to return for Visit 3 (Day 14±2 days)

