4.2.8.2. Missing Dates

If the start date/time of an AE is partially or completely missing, the date/time will be compared as far as possible with the date/time of the start of administration of study drug. The AE will be assumed to be treatment-emergent if it cannot be definitively shown that the AE did not occur or worsen during the treatment-emergent period (worst case approach). Listings will display the available date data.

The following general rules will be used:

- If the start time of an AE is missing but the start date is complete, an AE will only be excluded as being treatment-emergent if the start date is before the date of study drug administration or if the stop date/time is before study drug administration.
- If the start time and day are missing but the start month and year are complete, an AE will only be excluded as being treatment-emergent if the start month/year is before the month/year of study drug administration or if the stop date/time is before study drug administration.
- If the start day and month are missing but the start year is complete, an AE will only be excluded as being treatment-emergent if start year is before the year of study drug administration or if the stop date/time is before study drug administration.
- If the start date is completely missing, an AE will be considered treatment-emergent unless the stop date/time is before study drug administration.

The above general rules are applicable to the partially or completely missing worsening date/time of AE as well.

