4.8.2. Adverse Events

Adverse events will be coded using the Medical Dictionary for Regulatory Activities (MedDRA) and displayed in tables and listings using System/Organ/Class (SOC) and Preferred Term (PT).

Analyses of adverse events will be performed for those events that are considered treatment emergent, where treatment emergent is defined as any adverse event with onset after the first dose of study medication through the end of the study or any event that was present at baseline but worsened in severity.

Adverse events are summarized by subject incidence rates, therefore, in any tabulation, a subject contributes only once to the count for a given adverse event (SOC or preferred term) by treatment group and overall. In summary tables, SOC will be presented alphabetically and events within SOC will be presented by decreasing frequency count based on the total column.

The frequency and percentage of subjects with any treatment-related ocular and non-ocular TEAE, with any TEAE assessed by the Investigator as related to treatment (definite, probable, or possible relationship), with any TEAE by severity (mild, moderate or severe), and with any serious adverse event (SAE) will be summarized by treatment group and overall. In these tabulations, each subject will contribute only once (i.e., the most related occurrence or the most severe occurrence) to each of the incidence rates in the descriptive analysis, regardless of the frequency of episodes. Furthermore, the frequency and percentage of subjects with any TEAEs by outcome, with any TEAEs by action taken, with any TEAEs by action taken related to study drug will be also summarized in the table by treatment group and overall. Separate summaries will be performed for ocular and non-ocular TEAEs by the most severity and strongest relationship by SOC and PT by treatment group and overall.

Sponsor:	VivaVision Biotech, Inc.		
Protocol:	VVN001-CS-201		
Document Version No.:	V3.0	Document Date:	13-JAN-2022

No formal hypothesis-testing analysis of adverse events incidence rates will be performed.

All adverse events occurring on study will be listed in subject data listings.

By-subject listings also will be provided for the following: subject deaths; serious adverse events; and adverse events leading to withdrawal.

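### The start of the treatment-emergent period is not tied to the first double-masked dose, so adverse events from the vehicle run-in can be counted as TEAEs under the randomized arms

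*Protocol*

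**What the plan says.** Protocol 9.1.4 makes the TEAE summary the primary safety analysis and sets its start: "A TEAE will be defined as occurring after the first dose of IP". SAP 4.8.2 words it differently: "any adverse event with onset after the first dose of study medication through the end of the study". A second part of that definition, offered as an alternative, brings in baseline events that later become more severe. For incomplete onset dates, SAP 4.2.8.2 has the date "compared as far as possible with the date/time of the start of administration of study drug". Neither SAP term is defined. SAP Section 5 reports no change from the protocol's analyses, so the new wording cannot be read as a deliberate re-anchoring.

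The run-in product is vehicle, given for 14 days before randomization. Protocol 6.1.1 (Visit 1) says: "Subject will self-administer first dose of Single-Masked IP observed by trained study staff". Protocol 4.7.2 continues: "the subjects will self-administer the second dose of Single-Masked IP in the evening". Protocol 4.8.1 treats both products as IP: "Single-Masked and Double-Masked IP is contained in 3 mL single-use droppers". SAP 2.1.3 also calls the run-in product IP. At Visit 2, protocol 6.1.2 asks for "Occurrence of any AEs since the last visit", so run-in events enter the database.

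**The concern.** Safety and tolerability are the primary objective in SAP 1.2.1, so the main safety table should have one unambiguous start date. If the clock starts at Visit 1, events that arose on vehicle before randomization are attributed to the randomized arms. These events should be about equally common in all arms, so they carry no information on VVN001 and pull each active-versus-vehicle contrast towards no difference. Causality is also rated against IP (protocol 8.1.1). A run-in event judged possibly related could therefore appear as a treatment-related TEAE under 5% VVN001 in a subject who had not yet received VVN001.

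**Working it through.** **Step 1: the passages side by side**

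| Place | Usage | Points to |
|---|---|---|
| Protocol 4.7.2, 4.8.1, 6.1.1; SAP 2.1.3 | run-in vehicle called Single-Masked IP | Visit 1 |
| SAP Table 1 | the rows for IP administration and dispensing at Visit 1, and for study drug collection at Visit 2, carry the run-in footnote | Visit 1 |
| Protocol 4.7.2 | IP listed as the three randomized products | Visit 2 |
| Protocol 4.8.3 | run-in named separately from double-masked IP | Visit 2 |
| Protocol 4.9 | IP allocation is what is randomized | Visit 2 |
| SAP 4.6 | exposure counted within the treatment period | Visit 2 |
| SAP 4.8.2, second part | worsening from baseline (Day 1 in the efficacy sections) | Visit 2 |

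No sentence settles the matter.

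**Step 2: one event under each reading.** Suppose an event starts midway through the run-in in a subject later randomized to 5% VVN001. If run-in vehicle is IP, onset follows the first dose and the event is a TEAE in the 5% column. If the anchor is Visit 2, it is a TEAE only if it later worsens. The worsening part of SAP 4.8.2 is joined by *or*: it adds events and removes none.

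**Step 3: size.** The documents state no adverse event rate, so there is no figure of the plan's own to reproduce. All incidences below are assumptions. From the documents come the run-in (14 days), the treatment period (84 days) and 55 subjects per arm. On the literal reading the run-in is 14/98 = 14.3% of the counting window.

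Let p be a subject's TEAE risk over the 84 double-masked days and r the run-in risk, equal across arms and independent of p. The tabulated risk is q = 1 − (1 − p)(1 − r). The risk difference (RD) is then multiplied by (1 − r), and the risk ratio (RR) moves towards 1.

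*Constant rate*, with r taken from the vehicle risk: r = 1 − (1 − p_vehicle)^(14/84).

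- 30% versus 20%: r = 1 − 0.80^(1/6) = 0.0365. Vehicle: 1 − 0.80 × 0.9635 = 22.9%. Active: 1 − 0.70 × 0.9635 = 32.6%. RD goes from 10.0 to 9.6 points, RR from 1.50 to 1.42.
- 20% versus 10%: r = 1 − 0.90^(1/6) = 0.0174. Vehicle 11.6%, active 21.4%. RD goes from 10.0 to 9.8 points, RR from 2.00 to 1.85.

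Vehicle subjects counted with a TEAE only because of a run-in event: 2.92/22.92 = 12.7% in the first case and 1.57/11.57 = 13.5% in the second. In the first case this is 55 × 0.0292 = 1.6 subjects in the vehicle arm.

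*Run-in risk varied freely*, for 25% versus 10%:

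| r | Vehicle | Active | RD (points) | RR |
|---|---|---|---|---|
| 0 | 10.0% | 25.0% | 15.0 | 2.50 |
| 2% | 11.8% | 26.5% | 14.7 | 2.25 |
| 5% | 14.5% | 28.8% | 14.25 | 1.98 |
| 10% | 19.0% | 32.5% | 13.5 | 1.71 |
| 20% | 28.0% | 40.0% | 12.0 | 1.43 |

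**Step 4: against sampling error.** For 30% versus 20% with 55 per arm, the 95% half-width of the risk difference is 1.96 × √[(0.30 × 0.70 + 0.20 × 0.80)/55] = 16.1 points. The constant-rate shift of about 0.4 points is roughly 2% of that.

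**The case against.** The strongest reply is that the authors plainly meant Day 1. Protocol 9.1.3 leaves analysis detail to the SAP, and the SAP anchors on study medication rather than IP. Its exposure calculation is confined to the treatment period, and its worsening clause fits a Day 1 baseline better than a Visit 1 start. The Safety Set requires randomization plus at least one dose of IP. If run-in vehicle were IP, virtually every randomized subject would meet that second condition, so it would do no work. Onset date and time are recorded and all events are listed, so run-in events can be separated later. No adverse event test is planned.

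Most of this stands. A reader might infer that the plan definitely counts run-in events as treatment-emergent; the mixed usage in Step 1 does not support that. Evidence of intent is still not a definition, however. The SAP's own schedule applies its study drug label to the run-in product, so a programmer who followed the literal words would have textual support for a Visit 1 start.

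A reader might also infer that the FAS and SAF would change. They would hardly move, because the first double-masked dose is taken under observation in clinic at Visit 2.

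**Conclusion.** The point holds as an unanchored definition that, taken literally, can charge pre-randomization vehicle events to the randomized arms in the primary safety analysis. Two competent programmers could produce different tables from this text.

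It would go too far to say that the safety comparison is seriously diluted. Under a constant event rate the effect is modest: risk differences of 10.0 points become 9.6 to 9.8, and risk ratios of 1.50 and 2.00 become 1.42 and 1.85. In the 25% versus 10% example the loss becomes material at a run-in incidence of about 10% or more. That is conceivable, since the run-in is the first exposure to the drops and the start of artificial tear withdrawal, but the documents give no rate to support it. These figures assume equal run-in risk across arms and independence from later events. The consequence is confined to descriptive rates. The correction should be made because it is cheap and concerns the primary safety table.

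**What to change.** - In protocol 9.1.4 and SAP 4.8.2, define a TEAE as an adverse event with onset, or worsening in severity, on or after the first dose of Double-Masked IP at Visit 2.
- In SAP 4.2.8.2 and 4.8.5, define *study drug* by the same dose, so that the partial-date and concomitant medication rules share the anchor.
- List run-in events separately as pre-treatment events.
- For consistency only, use the same term in the FAS and SAF definitions in SAP 3.1.
- Record the clarification in SAP Section 5.

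The cost is a few sentences and one date variable in programming, with no new data collection planned. One check is worthwhile: protocol 4.8.3 asks sites to record the date and time of the first dose without naming the product. Confirm that the eCRF holds this for the first double-masked dose, because the time decides how events starting on the day of Visit 2 are classified.
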